interim analysis is negligible. If the methadone intervention contributes greater than normal adverse events (>2 patients) the study will be held from further recruitment. The study medication will not be administered further, no dosing changes will be made, and the IRB will be informed. A decision at this point will be reached regarding further accrual. If a patient should die prior to discharge, a thorough cause analysis will be implemented by the DSMB, the IRB, in addition to the analysis that will already be performed by the hospital. If it is due to the surgery outside of the trial mediation, the data for this patient will not be used and the information will be explicitly reported in any publication yet kept separated from the other patient's data, as it would not be feasible or make sense to include this patient in the analysis. If this adverse event is found to be caused by the methadone administration, the trial will be stopped. This is however an extremely unlikely scenario as methadone is used daily by millions of individuals, has already been approved by the FDA, and our study patients will undergo a rigorous screening, namely for QTc prolongation, to remove any potential risk of death as a result of methadone administration. The only wayy to address this possibility is to have a plan to remove this patient's data from the other patient's data, with a clear note made in the report.

Describe how possible confounding and/or effect modification will be addressed. The possible confounders have been addressed via the strict inclusion and exclusion criteria of the study. Other confounding variables including past narcotic usage, and a cutoff of <10mg equivalents of morphine will be considered when selecting patients for participation in this study. Such a low daily morphine dose is unlikely to significantly impact methadone effect or post-operative narcotic use in patients with this low level of narcotic usage compared to narcotic-naïve patients. Patient time to ambulation will be confounded by baseline neurological status and therefore we will randomly assigning patients to each arm of the study as described above. Confounding in regards to time of operative procedure and complexity of surgery will be controlled properly with appropriate randomization.

Describe how loss to follow up will be addressed

As described in previous sections, given that the intervention is a single intra-operative event, we do not anticipate any loss to follow-up within the standard post-operative care protocol. In the unlikely event any patient is lost to follow-up, we will attempt to contact the patients as is normal office procedure for post-surgical follow up. Portions of their data, especially those immediately relevant to the primary endpoints which pertain to their immediate post-operative hospitalization and experience may still be used, if complete up to patients discharge.

- 8) Data quality control and database management.
 - a) Describe methods for data entry and data management.
 - b) Describe the mechanism for checking and editing the data.
 - c) Describe computer data security and subject confidentiality. This is particularly important for multicenter studies.

Patient health data and records will be handled with compliance of HIPAA regulations and will only be accessed on Montefiore computers by members of the study as outlined by the IRB form. Patients identified from recruitment will kept in a list of enrolled patients in the study on a secure Montefiore drive. From there, all information will be taken from an enrolled patient's chart to a separate database and will be used in de-identified form only, with numbers assigned to each patient that are not related to patient MRN, and there will be no use of names or other personal identifiers. De-identified data will be used for database purposes but a password protected master list matching subject number to MRN and name will be kept by the principal investigator, allowing identification of patients, if requiredWe will use secure databases on encrypted Montefiore drives as our repository. They are safe, protected, and HIPAA compliant. Data will be checked by study personnel and edited in real-time on only Montefiore secured servers.

9) References: Include a bibliography of all references in the protocol.

Reference

1. Inturrisi CE. Pharmacology of methadone and its isomers. Minerva Anestesiol. 2005 Jul-Aug;71(7-8):435-7. Review. PubMed PMID: 16012416.

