Since the standard of care is narcotic usage to manage the significant pain that complex spinal surgery causes, it is understandable that methadone could be a desirable therapy to promote sustained pain control and early ambulation in these patients. It is our hypothesis that methadone use intraoperatively will result in earlier time to ambulate post op and better ability to participate with post-operative PT evaluation, lower narcotic usage, earlier discharge, and improved scores on clinical outcome scales including the Oswestry Low Back Pain Disability Questionnaire and the Short Form 36 Health Survery. It is also foreseeable that since methadone would be administered while the patient was sedated intraoperatively, it could prevent the association between the analgesia and euphoria that may result from self- or nurse-administered narcotics, such as with a PCA, which could promote early tolerance or reliance. Randomization of patients between methadone administration and standard intra-operative narcotic administration allows for controlled and accurate investigation of subjects compared to the current standard of care.

• Clearly state target population and recruitment methods

We would screen the first 200 consecutive patients to determine whether inclusion criteria are met, with an end goal of 120 patients who will complete the study and 60 control subjects who receive the current standard of care in a 1:1 randomized fashion. Patient will be recruited in office at time of consent for surgery by the principal investigator.

• State inclusion/exclusion criteria clearly

Inclusion criteria:

Patients undergoing elective lumbar transforaminal interbody fusion or lumbar laminectomy and posterolateral fusion will be enrolled in the study and consented for intraoperative single-dose methadone administration or standard narcotic regimen administration in a 1:1 block randomization plan. Patient may undergo one or two spinal level fusions and in blocks of 5, will be assigned to intervention or control groups in a manner that will be blinded to both the clinical team and the patients.

o Exclusion criteria:

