Age <21 or >80, renal failure requiring dialysis or serum creatinine greater than 2.0, significant hepatic dysfunction (liver function tests greater than twice the upper limit), hepatic cirrhosis, pulmonary disease requiring home oxygen therapy, obstructive sleep apnea, severe heart disease, allergy to methadone, morphine, ketamine or fentanyl, **recent or distant history of opioid abuse,** opioid use equal to or greater that the equivalent of 10mg morphine per day, poorly managed psychiatric illness, a known history of alcohol abuse, morbid **obesity (for the purposes of this study body mass index > 50 kg/m2),** treatment with other NMDA receptor antagonists, HIV-1 protease inhibitors, erythromycin or ketoconazole, prolonged QTc on pre-operative EKG, and the refusal or inability to sign the consent form to agree to participate in this study.

State primary and secondary outcome(s)

The primary outcomes for the study include total narcotic dose post-operative, frequency of narcotic use, the time to first ambulation after surgery with PT, length of stay, disposition (i.e. level of rehabilitative care), and improvement on clinical questionnaires in the intervention group as compared to the control group. Secondary outcomes include better subjective pain control, need for post-operative course of

dexamethasone for post-operative/post-fusion radiculopathy or neurapraxia/neuropathy and fusion at 3-6 months.

> For Randomized clinical trials

• Indicate whether a parallel or crossover study, and the number of treatment groups
The study will take the form of a parallel, 2 arm analysis of a methadone treatment group or a
group receiving the current standard of care without intra-operative methadone administration.

• Describe randomization and blinding procedures

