case and will administer a 0.2 mg/kg single-dose administration of methadone on incision (not to exceed 20 mg, as used in the literature) with a ketamine infusion of 4 µg/kg/min and a remifentanil infusion starting at 0.1 µg/kg/min and titrating to effect or sufentanil infusion starting with a dose of 0.3 µg/kg/hr and titrating to effect. These standard doses have been well documented and studied in the literature as demonstrated above and will be overseen and have been approved by board certified anesthesiologist. For lengthier procedures, there will not be re-dosing of narcotics toward the end of the procedure. The operative procedure will not be altered in any way for the purposes of this study, and is beyond the scope of this protocol, yet can be detailed as requested. The patient will be taken to the recovery room postoperative and will be put on a standard post-operative morphine PCA as used in our department at a rate of 1mg per 6 minute lock-out period. This standard dose and therapy has been used in nearly all postoperative lumbar fusion patients to date. Patient's narcotic usage and pain rating will be recorded at the intervals listed above and when stable from a cardiovascular standpoint, will be transition to the neurosurgery floor. Once able to bare weight, the patient will be encouraged to work with physical and occupational therapy as per standard post-operative protocol. One the patient uses the PCA at a rate of less that once an hour, and can be managed with oral pain medications, the PCA will be removed. The remainder of their post-operative care will be according to the standard departmental protocol, and when milestones such as ambulation, voiding, and pain control are met, they will be discharged either to home, an acute care facility, or a subacute rehabilitation center. Per standard of care, the patients will return to the clinic at 2 weeks and 3 months as part of their routine clinical care. Any adverse events/reactions will be recorded and managed as normally they would be, and naloxone will be available for suspicion of narcotic overdose. Patient assigned to the control group will be monitored in the manner post-operatively, as is the standard of care for all of our patients.

Define the outcome measures pertaining to each aim.

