The sample size was determined using the Gottschalk study listed in the reference section which used methadone vs. sufentanil in 29 patients undergoing lumbar fusion surgery and the measures for pain level and total narcotic usage at 48 hours to determine an 'n' for the total study population, using a power of 0.80. The details of the calculations is listed in the data analysis section (7a) below and calculated with the suggestion of the statistician on the IRB. The assumptions with which the outcomes are hypothesized are the result of previously published data using similar populations. Two sample t-tests are appropriate to determine statistical significance between mean pain scores between different patients in the control and study groups for each individual time point as there will be no censoring of the study data. Ranked T-test may also be used if outliers are present, however patients with unusual post-operative courses may be excluded if their reason for prolonged hospitalization is unrelated to immediate post-operative pain

control. The large sample size plans to take into account possible outliers that may not be included in final analysis, despite their mention in study write-up to determine why their post-operative hospitalization was prolonged. Additionally, data about patients' mean time to ambulation, mean time to discharge, and mean overall narcotic usage will be measured between the control and study populations. Data analysis will be performed with the assistance of the biostatistician listed as a member of the study team, [name], from the Albert Einstein College of Medicine, Division of Biostatistics. Thus, a sample of 60 completed methadone patients will be evaluated against 60 randomized, standard narcotic regimen controls. The mean data for control patients' pain ratings, narcotic usage, time to ambulation, and time to discharge will be obtained, the statistical deviation of this data will be measured and compared to subject data in all facets.

• Take into account anticipated drop-out or loss-to-follow up rate.

We intend to screen 200 patients to have 60 in each arm ultimately included in the study. Since the intervention is a single intra-operative occurrence, that when completed patients cannot reverse, we do not anticipate any drop-out. A two week follow-up visit is a required standard of care for all post-operative patients, without patient loss to follow-up historically. The study is completed at this point.

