Two sample T-tests will be performed to evaluate continuous variables such a total morphine dose, pain level per VAS, time to first morphine dose, time to ambulation, and time to discharge. The assistance of a statistician, [name], from the Albert Einstein College of Medicine, Division of Biostatistics will be used for statistical analyses performed in this study. Wilcoxon Rank Sum Test will be used if outliers are noted in the study population, detected as more than 5 MAD from the median, and a concern presents that single patients may skew the data. Additionally, review of these patients who are outliers may also necessitate their exclusion from this work if they provide data that will significantly modify the mean of the remaining patients. This can be accounted for in the goal of 60 patients to be accrued in each arm of the study. A thorough explanation and review will performed on any such patients in any form of write up of this work.

At least one study hypothesis (or a statement that the study is hypothesis-generating or a feasibility study):

The use of single dose intraoperative methadone will decrease total narcotic usage, time to ambulation, mean pain rating at 24 and 48 hours and will decrease number of days of hospitalization compared to sufentanil (current standard of care) controls.

• A statement regarding specifically what data are to be used to test the hypothesis (or to generate the hypotheses)

We will obtain data of total narcotic usage, days until patients ambulate with physical therapy, pain ratings at 24 and 48 hours, and days to discharge, all obtained from the patient's medical record.

- o The statistical method(s) to be used to test the hypothesis with that data
 Two-sample T-test will be used with the assistance of an Albert Einstein statistician, [name], to analyze
 the above data and determine if there is statistical significance between the two groups, in addition to the
 stipulations outlined above to address outlier patients.
- A power analysis to determine the sample size (even for pilot studies)

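### Six unranked primary outcomes, with no deciding outcome, testing order, alpha split or success rule for the final analysis, and sections that disagree on which outcome leads

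*Combined protocol and SAP*

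**What the plan says.** - **Section 2, primary and secondary outcomes.** The list opens "The primary outcomes for the study include total narcotic dose post-operative, frequency of narcotic use, the time to first ambulation after surgery with PT" and goes on to length of stay, disposition and improvement on clinical questionnaires. That is six outcomes, none given priority. Pain is placed lower: "Secondary outcomes include better subjective pain control".
- **Section 2, objectives.** The questionnaire outcome covers at least two instruments: "improved scores on clinical outcome scales including the Oswestry Low Back Pain Disability Questionnaire and the Short Form 36 Health Survery". Six is therefore a minimum count.
- **Section 3, sample size.** The number of patients is said to rest on a prior randomised study and "the measures for pain level and total narcotic usage at 48 hours".
- **Section 7a, methods.** "Two sample T-tests will be performed to evaluate continuous variables such a total morphine dose, pain level per VAS, time to first morphine dose", continuing with time to ambulation and time to discharge. The list is illustrative. Disposition, which is categorical, has no named test.
- **Section 7a, hypothesis.** Methadone "will decrease total narcotic usage, time to ambulation, mean pain rating at 24 and 48 hours and will decrease number of days of hospitalization". The data statement matches: "data of total narcotic usage, days until patients ambulate with physical therapy, pain ratings at 24 and 48 hours, and days to discharge". Frequency of narcotic use, disposition and questionnaires are absent, and pain is present.
- **Section 7a, power.** Power is given in SD units (0.56 and 0.74) at level 0.05. It is translated into natural units only for time to discharge, with an SD of 6.7 days.
- **Section 7, interim analyses.** The only Type I error statement covering several measures concerns the look after 20 patients.

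**The concern.** A plan with several primary outcomes has to say what counts as a positive trial. This one does not. As written, a p-value below 0.05 on any one of three to six outcomes could be reported as a positive primary result. A reader could not tell which outcome was meant to decide. If every outcome had to succeed, the stated power, which is for a single test, would be too high. The rest of the plan does not settle the matter, because each section points to a different lead outcome.

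**Working it through.** **1. The plan's own figure.** Inputs from Section 7a: effect 0.56 SD, power 80%, level 0.05, 51 per group calculated, 60 per group planned.
- Two-sided: n = 2(z₀.₉₇₅ + z₀.₈₀)²/d² = 2(1.960 + 0.842)²/0.56² ≈ 50.1, rounded up to 51. The t-based value is 51.03. The stated 51 reproduces.
- One-sided: 2(1.645 + 0.842)²/0.56² ≈ 39.4, rounded up to 40. The plan does not state sidedness, but 51 fits only a two-sided test. One test therefore carries 2.5% error in the direction of benefit.
- At 60 per arm the noncentrality is 0.56 × √(60/2) = 3.07, and the t-test power is 86.0%.

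**2. The outcome lists side by side.**

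| Outcome | Section 2 | Section 3, sample size | Section 7a hypothesis | Section 7a power |
|---|---|---|---|---|
| Narcotic dose | primary | yes (48 h) | yes | – |
| Frequency of use | primary | – | – | – |
| Time to ambulation | primary | – | yes | – |
| Length of stay | primary | – | yes | yes (SD 6.7 days) |
| Disposition | primary | – | – | – |
| Questionnaires | primary | – | – | – |
| Pain | secondary | yes (48 h) | yes (24 h, 48 h) | – |

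Three plausible families follow: six (Section 2), five (the Section 7a hypothesis, counting pain twice), and three (narcotic dose, ambulation and length of stay, common to both).

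**3. If any one outcome can be claimed.** Assumptions: each test at two-sided 0.05, jointly normal statistics with a common correlation ρ, and no true difference. The documents give no correlations, so ρ runs from 0 to 0.9. With c = 1.960, the chance of at least one false claim of benefit among k tests is

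1 − ∫ Φ((c − √ρ·u)/√(1−ρ))ᵏ φ(u) du,

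which at ρ = 0 is 1 − 0.975ᵏ.

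| k | ρ = 0 | 0.5 | 0.7 | 0.9 |
|---|---|---|---|---|
| 6 | 14.1% | 10.4% | 8.2% | 5.4% |
| 5 | 11.9% | 9.2% | 7.4% | 5.1% |
| 3 | 7.3% | 6.3% | 5.5% | 4.2% |
| 1 | 2.5% | 2.5% | 2.5% | 2.5% |

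Counting the two questionnaires separately (k = 7) gives 16.2% down to 5.7%.

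**4. If all must succeed.** Assume a true 0.56 SD effect on every outcome and 60 per arm, so each test has power 0.860 and b = Φ⁻¹(0.860) = 1.082. Joint power is ∫ Φ((b + √ρ·u)/√(1−ρ))ᵏ φ(u) du, which at ρ = 0 is 0.860ᵏ.

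| k | ρ = 0 | 0.5 | 0.7 | 0.9 |
|---|---|---|---|---|
| 3 | 64% | 71% | 75% | 80% |
| 5 | 47% | 62% | 69% | 77% |

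**5. What one primary would support.** At 60 per arm and two-sided 0.05, 80% power is reached at 0.516 SD. For length of stay that is 0.516 × 6.7 = 3.46 days.

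**The case against.** **The lists are conjunctive.** Section 2 joins the outcomes with *and*, and so does the Section 7a hypothesis. If all must succeed there is no inflation. A reader might equally infer that any one success is enough and that the trial therefore runs a 14% error rate. The documents support neither inference, because ordinary list grammar is not a success rule. This part of the objection stands: the percentages are conditional and only illustrate the gap.

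**The sample size does name outcomes.** A reader might conclude that the powered outcome is nowhere identified. That goes too far. Section 3 names pain and narcotic usage at 48 hours, and Section 7a translates its effect size into days to discharge. The fault is that the two conflict. For the same reason, length of stay cannot be taken as the implied primary: Section 2 gives it no priority, and Section 3 bases the numbers on something else.

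**The six-test figure assumes tests that are not specified.** Section 7a names no test for frequency of use, disposition or questionnaires. This stands, and is why the five- and three-test families are shown beside it.

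**The model is idealised.** It does, and one common correlation with normal statistics fits categorical disposition poorly. Independence is implausible for narcotic dose with frequency of use, or for ambulation with length of stay. The upper ends are therefore unlikely to apply. At a correlation of 0.9 the rate for three to six outcomes is still 4–5%, against 2.5%.

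**Conclusion.** The concern holds as a missing decision rule combined with conflicting lead outcomes. That part needs no assumption: there are six unranked primaries, nothing says what makes the final analysis positive, and the hypothesis, the sample-size basis and the power paragraph point to different outcomes.

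Its size depends on the rule the team adopts. Under an any-one rule, false claims of benefit run at roughly two to six times the single-test rate. Under an all-must-succeed rule, the cost is power below the 86% that one test would have. Both rest on two-sided 0.05 per test and assumed correlations; the power figures also assume 0.56 SD on every outcome. It would be wrong to report that the trial has an inflated error rate as a fact, since no any-one rule is written. The gap deserves correction because it decides what the trial can conclude, and because correcting it costs little.

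**What to change.** Before unblinding, and without sight of the interim comparison of the arms, name **one primary outcome**, tested at two-sided 0.05. State its time window, test, assumed SD and power. The text offers three candidates, and the choice is the team's:
- **Length of stay.** The only outcome with a stated SD.
- **Total post-operative opioid dose.** It needs an SD, a time window (48 hours appears only in Section 3) and an opioid conversion rule. Section 7a tests total morphine dose, yet Section 2 says that once a patient's PCA use is low and the patient "can be managed with oral pain medications, the PCA will be removed".
- **Time to first ambulation.** It is in the title and the Section 2 hypothesis, and needs an SD.

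Make the other five Section 2 outcomes, and pain at 24 and 48 hours, secondary. Test them for confirmatory claims **only if the primary succeeds**, in a fixed order or by Holm; otherwise label them exploratory. Without that gate, a primary and a separate family each at 0.05 could together allow about 1 − 0.975² = 4.9% false claims of benefit if independent. Give disposition a categorical or ordinal test. Use the same list in the outcome, sample-size, hypothesis, power and interim text.

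**Cost.** Wording only, with no added patients or visits. The other outcomes support no confirmatory claim if the primary fails. Under Holm across five, the first step is 0.05/5 = 0.01, where a 0.56 SD effect has 67% power at 60 per arm, against 86% at 0.05. It is lower still if pain joins the family. A fixed order carries no such penalty for its first outcome.
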